Safety summaries (tables, figures) on the Safety set (respectively on the Switch Analysis Set) include only data from the on-treatment (resp. on-switched treatment) period with the exception of baseline data which will also be summarized where appropriate (e.g. change from baseline summaries). In particular, summary tables for adverse events (AEs) will summarize only on-treatment (resp. on-switched treatment) events, with a start date during the on-treatment (resp. on-switched treatment) period (**treatment-emergent** AEs) (resp. switched-treatment-emergent AEs). In addition, a separate summary for death including on-treatment and post-treatment deaths will be provided.

However, all safety data (including those from the pre-treatment, post-treatment and post-switched treatment period) will be listed and flagged as appropriate.

Efficacy summaries on the FAS (apart from OS and PFS) include data from baseline up to either the last assessment on or before the EoT visit or before or on treatment failure, whichever is the earliest.

Efficacy summaries on the Switch Analysis Set include data from baseline_switch up to the last assessment on or before the S-EoT visit or before or on treatment failure during the switched treatment period, whichever is the earliest.

The efficacy assessments collected post-treatment failure, post-EoT or post S-EoT visit are not included in any efficacy analyses (except for OS and PFS analyses). However, they will be listed and flagged as appropriate.

Windows for multiple assessments

Data such as molecular response, cytogenetic response collected over time (including unscheduled visits) will be summarized by scheduled time point. As patients do not always adhere to the visit schedule, visits will be remapped according to visit windows defined in Tables 2-1 to Table 2-4 of this document to enable by-visit analysis. Only those protocol-defined visits will have the visit window defined. Each assessment (including the end of treatment assessment), either scheduled or unscheduled, will have a mapped visit assigned, as long as study day is available, according to the defined visit window up to the date with data included.

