If more than one assessment is assigned to the same time window, the assessment performed closest to the target date will be used for by-visit statistical analyses. If 2 assessments within a visit window are equidistant from the target date, then the average of the 2 assessments will be used. If multiple assessments on the same date, then the the average will be used. Data from all assessments (scheduled and unscheduled), including multiple assessments, will be listed.

Table 2-1 Time windows for molecular response

Assessment	Target day of assessment	Time Interval
Baseline	≤ 1	≤ Day 1 [#]
Week 4	29	Day 2 to day 43
Week 8	57	Day 44 - 71
Week 12	85	Day 72 - 99
Week 16	113	Day 100 to day 141
Week 24	169	Day 142 to day 211
Week k (k=36, 48, ...)	$k \times 7 + 1$	Day $k \times 7 - 40$ – $k \times 7 + 43$

Day 1 = Date of randomization
EOT assessments are mapped to the time points as needed.

Table 2-2 Time windows for cytogenetic response

Assessment	Target day of assessment	Time Interval
Baseline	1	≤ Day 1 [#]
Week 24	169	Day 2 to day 253
Week 48	337	Day 254 to day 421
Week 72	505	Day 422 to day 589
Week 96	673	Day 590 to day 700

Day 1 = Date of randomization
EOT assessments are mapped to the time points as needed.

For PRO data time windows will be defined for descriptive summary by visit and longitudinal data analysis. If more than one assessment is available in the same time window, the assessment closest to the planned date will be considered. If two assessments are obtained with the same time difference compared to the scheduled visit day, the assessment obtained prior to visit will be considered.

Table 2-3 Time windows for PRO: MDASI-CML, EQ-5D-5L, PGIC

Assessment	Target day of assessment	Time Interval
Baseline	1	≤ Day 1 [#]
Week 4	29	Day 2 - 43
Week 8	57	Day 44 - 71
Week 12	85	Day 72 - 99
Week 16	113	Day 100 - 141
Week 24	169	Day 142 - 211
Week 36	253	Day 212 - 295
Week 48	337	Day 296 - 505
Week 96	673	Day 506 - 700

Day 1 = Date of randomization

Table 2-4 Time windows for PRO: WPAI-CML

Assessment	Target day of assessment	Time Interval
Baseline	1	≤ Day 1 [#]
Week 4	29	Day 2 - 57
Week 12	85	Day 58 -127
Week 24	169	Day 128- 253
Week 48	337	Day 254 - 505
Week 96	673	Day 506 - 700

Day 1 = Date of randomization

Here's the general rule for the target day of assessment and time interval: For Week k visit, target day of assessment is defined as $k*7+1$. For the time interval, "Lower limit" = "upper limit

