of prior applicable visit" +1. "Upper limit" = "target day of current visit" + integer part of ("target day of next applicable visit" – "target day of current visit")/2.

Visit window for the switched treatment period will use the same rules as described above but with Day 1 being the date of first administration of asciminib. Visit name for the switched treatment period will be defined similarly with annotated by beginning with "S-" (e.g. S-Week 4) to differentiate from those used for the randomized treatment period.

Last contact date

The last contact date will be derived for patients not known to have died at the respective analysis data cut-off date using the last complete date among the following:

Table 2-5 Last contact date data sources

Source data	Conditions
Date of randomization	No condition
Last contact date/last date patient was known to be alive from Survival Follow-up page	Patient status is reported to be alive, lost to follow-up or unknown
Start/End dates from further antineoplastic therapy	Non-missing medication/procedure term
Start/End dates from drug administration record	Non-missing dose. Doses of 0 are allowed
End of treatment date from end of treatment page	No condition
Any specific efficacy (molecular or cytogenetic) assessment date if available	Evaluation is marked as 'done'
Laboratory/PK collection dates	Sample collection marked as 'done'
Vital signs date	At least one non-missing parameter value
Performance status date	Non-missing performance status
Start/End dates of AE	Non-missing verbatim term

The last contact date is defined as the latest complete date from the above list on or before the respective data cut-off date. The cut-off date will not be used for last contact date, unless the patient was seen or contacted on that date. No date post the cut-off date will be used. Completely imputed dates (e.g. the analysis data cut-off date programmatically imputed to replace the missing end date of a dose administration record) will not be used to derive the last contact date.

The last contact date will be used for censoring of patients in the analysis of overall survival.

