2.11 Patient-reported outcomes

The FAS will be used for analyzing PRO data unless specified differently. The MDASI CML, PGIC along with EQ-5D-5L will be used to assess patient's disease-related symptoms and health-related quality of life from baseline to EOT; and the WPAI-CML will be used to assess work productivity and activity impairment related to the patient's CML. All tools require patient's direct completion and will be administered utilizing electronic device for data collection at scheduled time points from screening to end of treatment.

The baseline is defined in [Section 2.1.1](#). Patients with an evaluable baseline score and at least one evaluable post-baseline score during the treatment period will be included in the change from baseline analyses. Missing data items in a scale will be handled according to the manual for each instrument. No imputation will be applied if the total or subscale scores are missing at a visit. All measures will assess differences between the treatment arms.

Compliance to the schedule of administration of each PRO questionnaire will be summarized by treatment group, for baseline and scheduled post-baseline assessment time points. The following categories, as collected on the eCRF, will be used to describe whether the questionnaire was completed at a specific time point:

1. yes, fully completed
2. yes, partly completed
3. no

Repeated measures model for continuous scores

To best utilize the repeated assessments of a given PRO score, a repeated measures model for longitudinal data will be used to estimate differences between treatment arms. This repeated measures model will include terms for treatment, the stratification factor (major cytogenetic response status), time, baseline value as main effects, and an interaction term for treatment by time. This analysis will be restricted to patients with an evaluable baseline score and at least

one evaluable post-baseline score. All data collected until end of treatment (including the end of treatment assessment) will be included in the analysis. Note that only data collected under treatment (i.e. while the patient is treated) will be included. The end of treatment assessment will be included if collected within 7 days of the last dose intake.

Time will be considered as a continuous variable expressed in weeks, i.e. considering that the PRO score follow a linear trend.

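### Week 96 windows for marrow and PRO data stop at Day 700 while the PCR window runs to Day 715, and early end-of-treatment questionnaires are summarised as Week 96

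*Combined protocol and SAP*

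**What the plan says.** The relevant text is Section 2.1.1 of the current SAP (Addendum 1.0, October 2020), under the windows for multiple assessments; Amendment 3 has the same tables.

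- Target day: "For Week k visit, target day of assessment is defined as $k*7+1", so Week 96 is Day 673. Each window's upper limit is its target plus the integer part of half the gap to the next applicable visit. The next window starts the day after.
- Table 2-1 (PCR): Week k, from Week 36 on, runs from Day 7k-40 to Day 7k+43.
- Table 2-2 (cytogenetics): Week 96 is "Day 590 to day 700".
- Tables 2-3 and 2-4 (PROs), for which "time windows will be defined for descriptive summary by visit and longitudinal data analysis": Week 96 is Days 506-700. Week 48 is Days 296-505 in Table 2-3 and Days 254-505 in Table 2-4 (WPAI, which has no Week 36 visit).
- Mapping: "Each assessment (including the end of treatment assessment), either scheduled or unscheduled, will have a mapped visit assigned, as long as study day is available". This sentence covers Tables 2-1 to 2-4.

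Section 2.11 governs the PRO model. It includes only data collected under treatment, and of the EOT assessment it says: "The end of treatment assessment will be included if collected within 7 days of the last dose intake". On time it says: "Time will be considered as a continuous variable expressed in weeks".

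Section 2.7.3 makes patients who discontinue before a time point non-responders for MMR and CCyR at that time point. Section 5.4.2 groups missing cytogenetic evaluations with non-response. Section 5.5.2 bounds the 'by' rates at the end of the visit window.

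**The concern.** Two separate problems arise at Week 96.

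On the late side, one clinic visit can be in window for PCR and out of window for marrow and questionnaires. Section 2.7.1.2 makes the asymmetry sharper. A patient in MMR with no marrow is credited with CCyR at that time point, so a Day 705 PCR can establish Week 96 CCyR, while a Day 705 marrow with 0% Ph+ metaphases cannot. Marrow is required only of patients not in MMR, so the loss falls on those for whom marrow is the only evidence of CCyR.

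On the early side, PROs are scheduled at Weeks 48 and 96 with nothing between. A questionnaire on Days 506-631 is therefore likely to be an EOT or unscheduled one. The closest-to-target rule does not remove it, because a patient who has stopped has no later on-treatment value. MMR and CCyR have a rule for discontinuers; the PROs have none. The descriptive Week 96 PRO summary can thus combine patients near Week 96 on treatment with patients measured months earlier as they stopped.

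**Working it through.** **Inputs.** Targets and the midpoint rule from Section 2.1.1; visit schedules from Tables 2-1 to 2-4 and Sections 2.11.1 to 2.11.4.

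**Step 1: reproduce the plan's limits.** Upper limit = target + int((next target - target)/2).

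- Cytogenetics: Week 24, 169 + 84 = 253; Week 48, 337 + 84 = 421; Week 72, 505 + 84 = 589. All match Table 2-2.
- PRO Week 48: 337 + int((673 - 337)/2) = 337 + 168 = 505. Matches Tables 2-3 and 2-4.
- PCR Week 96, next visit Week 108 (Day 757): 673 + int((757 - 673)/2) = 673 + 42 = 715. Matches 7 x 96 + 43 = 715. The lower limit is 7 x 96 - 40 = 632.

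The rule reproduces every limit except Day 700. It defines no upper limit for a last visit. Day 700 is target + 27, which would need a next visit 54 or 55 days later (Day 727 or 728), and none is scheduled. Continuing the previous spacing would give Day 757 for cytogenetics (next visit Week 120) and Day 841 for PROs (next visit Week 144).

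One plausible origin is carry-over. Between the 2017 SAP and the current one, the cytogenetic limits moved from 248/416/584 to 253/421/589 and the PRO Week 48 limit from 500 to 505, each by 5 days. Day 700 alone did not move. This is inference, not something the SAP says.

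**Step 2: width of the Week 96 windows.**

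| Series | Window (days) | Earliest | Latest |
|---|---|---|---|
| PCR, Table 2-1 | 632-715 | 673 - 632 = 41 early | 715 - 673 = 42 late |
| Cytogenetics, Table 2-2 | 590-700 | 673 - 590 = 83 early | 700 - 673 = 27 late |
| PROs, Tables 2-3 and 2-4 | 506-700 | 673 - 506 = 167 early | 700 - 673 = 27 late |

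**Step 3: late gap.** 715 - 700 = 15 days (701-715) on which a PCR maps to Week 96 and a marrow or questionnaire maps to nothing.

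**Step 4: early labels.** A PCR on Day 506 maps to Week 72 (Days 464-547), and one on Days 548-631 to Week 84. A questionnaire on any of those days from 506 on maps to Week 96, up to 167/7 = 23.9 weeks before target.

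**Step 5: possible effect on the PRO summary.** If a share p of an arm's Week 96 values are early EOT values, and these score d points worse, the between-arm difference in means shifts by d x (p for bosutinib - p for asciminib). The documents give no p or d. Purely as an assumption, take 30 bosutinib and 95 asciminib Week 96 values and d = 1 point, with the same number of early EOT values in each arm:

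- 0 per arm: shift 0
- 3 per arm: 3/30 - 3/95 = 0.100 - 0.032 = 0.07 points
- 6 per arm: 6/30 - 6/95 = 0.200 - 0.063 = 0.14 points

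If the shares are equal in the two arms, the shift is zero whatever d is.

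**The case against.** The strongest reply is that the early limits, 590 and 506, are what the prespecified midpoint rule gives for visits 24 or 48 weeks apart, and that contiguous windows keep data. That stands: these limits are not errors under the rule. For cytogenetics the discontinuation rule also protects the CCyR rates at Week 96. What remains is that the PROs use the same wide window without such a rule.

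Several stronger readings are tempting but not supported.

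- **Late marrows are thrown away.** They are not. All assessments are listed, and time to CCyR and duration of CCyR are defined on dates, not windows. The loss is confined to the Week 96 CCyR rate and category, and to CCyR by Week 96 when it is first documented on Days 701-715.
- **The longitudinal PRO model is distorted.** Section 2.11 does not say whether time is the actual or the mapped week. Section 2.1.1 says the windows serve longitudinal analysis, and an unstructured correlation matrix suggests discrete visits, so mapped time is a natural reading, but not a stated one. EOT values enter only if collected within 7 days of the last dose, so they are on-drug or nearly so. That limit is not stated for the descriptive tables.
- **The Week 48 PRO summary is equally affected.** A patient with a questionnaire near Day 337 keeps it under the closest-to-target rule, so a later EOT value matters only when the Week 48 visit was missed.
- **The PRO comparison is biased towards one arm.** No counts support this; the figures in Step 5 are assumptions.

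Frequency is also unknown. The protocol's permitted visit windows (Section 7.1.5) are not in the part available. The 96-week cut-off is 96 weeks after the last patient's first dose, so for the last patients enrolled, visits on Days 701-715 fall outside that analysis in any case.

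**Conclusion.** The point holds in limited form. Day 700 in Tables 2-2 to 2-4 does not follow from the SAP's rule and leaves a 15-day stretch in which PCR counts for Week 96 and marrow and questionnaires do not. In that stretch, a patient with CCyR but not MMR is misclassified as a Week 96 CCyR non-responder. EOT questionnaires from Days 506-631 are labelled Week 96 in the descriptive PRO tables, up to 167 days early. An effect on the PRO model requires that time be the mapped week, and is then limited to EOT values within 7 days of the last dose.

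CCyR is a non-key secondary endpoint with descriptive p-values, and the PROs are exploratory. MMR at Weeks 24 and 96 uses Table 2-1 and is untouched, so no confirmatory conclusion depends on this. The case for acting is that the misclassification is avoidable at almost no cost.

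**What to change.** Before the 96-week database lock:

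1. End the Week 96 window at Day 715 in Tables 2-2, 2-3 and 2-4, to match Table 2-1.
2. In the descriptive PRO tables, show EOT questionnaires from Days 506-631 in a separate EOT row, not as Week 96.
3. Leave the Week 48 lower limits as they are: Day 296 in Table 2-3 and Day 254 in Table 2-4. Imposing Day 296 on WPAI would leave Days 254-295 in no window.
4. State in Section 2.11 that time in the repeated-measures model is the actual assessment time in weeks.

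This needs table edits, one sentence and re-mapping, with no new data. The cost is fewer values labelled Week 96 and a Week 96 PRO summary closer to patients still on treatment. That has its own selection, and the report should say so.

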2.2 Analysis sets

Full Analysis Set

The Full Analysis Set (FAS) comprises all patients to whom study treatment has been assigned by randomization. According to the intent to treat principle, patients will be analyzed according to the treatment and stratum they have been assigned to during the randomization procedure.

Safety Set

The **Safety Set** includes all subjects who received at least one dose of study treatment. Subjects will be analyzed according to the study treatment actually received.

The actual treatment received corresponds to:

- the randomized treatment if patients took at least one dose of that treatment;
- the first treatment received if the randomized treatment was never received.

Pharmacokinetic Analysis Set

The **Pharmacokinetic Analysis Set (PAS)** includes all patients who provide at least one evaluable PK concentration. For a concentration to be evaluable, patients are required to:

- Take a dose of asciminib prior to sampling
- Take the same dose of asciminib for at least 3 consecutive days without dose interruption or dose modification prior to sampling
- Have the pre-dose sample collected before the next dose administration

Other analysis sets

- For duration of MMR and time to MMR (descriptive analysis), the **MMR Responder Set** will be used that is a subset of FAS and includes patients who achieve MMR at any time on study treatment.
- For CCyR rates at and by scheduled time points and time to CCyR (Kaplan-Meier analysis), the **CCyR Analysis Set** will be used that is a subset of FAS and includes patients who are not in CCyR at baseline.
- For duration of CCyR and time to CCyR (descriptive analysis), the **CCyR Responder Set** will be used that is a subset of FAS and includes patients who do not have CCyR at baseline and achieve CCyR at any time on study treatment.
- For analyses of patients switched to asciminib, the **Switch Analysis Set** will be used that is a subset of FAS and includes patients who switched from bosutinib to asciminib and received at least one dose of asciminib.

Patient Classification

Patients may be excluded from the analysis populations defined above based on the protocol deviations entered in the database and/or on specific subject classification rules defined in [Table 2-6](#).

Table 2-6 Subject classification based on protocol deviations and non protocol deviation criteria

Analysis set	Protocol deviations leading to exclusion	Non protocol deviation leading to exclusion
FAS	No written inform consent	Not applicable
Safety set	No written inform consent	No dose of study medication
PK analysis set	No written inform consent	See definition of PAS
MMR Responder Set	Not applicable	See definition of MMR Responder Set
CCyR Analysis Set	Not applicable	See definition of CCyR Analysis Set
CCyR Responder Set	Not applicable	See definition of CCyR Responder Set
Switch Analysis Set	Not applicable	See definition of Switch Analysis Set

Withdrawal of Informed Consent

Any data collected in the clinical database after a subject withdraws informed consent from all further participation in the trial, will not be included in the analysis. The date on which a patient withdraws full consent is recorded in the eCRF.

2.2.1 Subgroup of interest

Subgroup analyses will use the same method as for the analysis in the respective overall analysis set.

The objective for carrying out these subgroup analyses is to identify potential issues that may be limited to a subgroup of patients, or that are more commonly observed in a subgroup of patients.

Summary tables and figures will be generated only for subgroups with at least 15 patients.

Efficacy

The primary efficacy endpoint will be summarized by the following subgroups to examine the homogeneity of treatment effect provided that the primary efficacy analysis based on the FAS is statistically significant:

- Stratification factor (based on randomization data from Interactive Response Technology [IRT]): “Major Cytogenetic Response” or “No Major Cytogenetic Response”
- Stratum reported in the CRF (derived using the data collected on the Bone Marrow Aspirate eCRF at baseline: see Appendix): “Major Cytogenetic Response” or “No Major Cytogenetic Response”

- Sex: Female or male
- Race: Asian, Caucasian, or others
- Age category (≥ 18 -< 65 years, ≥ 65 years, ≥ 75 years,)
- Reason for discontinuation of the last prior Tyrosine Kinase Inhibitor (TKI): Failure (i.e. lack of efficacy) or intolerance (i.e. adverse event, lack of tolerability).
Note: Only one reason for discontinuation is allowed for each prior therapy.
- Number of prior TKI therapies: 2, 3 or ≥ 4
- Line of therapy of randomized treatment: 3rd, 4th or $\geq 5^{\text{th}}$
- With or without Week 1 Day 1 BCR-ABL1 mutation (other than T315I or V299L) by Sanger Sequencing at central lab: Wild type or mutant
- BCR-ABL ratio at baseline $\geq 1\%$ or $<1\%$

No formal statistical test of hypotheses will be performed for the subgroups, only point estimate of the treatment effect and 95%-confidence intervals will be provided (see [Section 2.14](#) for further analysis details). The objective of the efficacy subgroup analysis is to demonstrate homogeneity of treatment effect in the above subgroups.

Safety

Subgroup analyses for selected safety endpoints will be defined when required.

Japan-specific subgroup analyses

Two subgroups will be formed based on geographic region: Japan or other region (this is not based on ethnicity). These subgroup analyses will be only used for submission to Japan health authority.

Summary tables and figures will be presented for the two subgroups for the following outcome measures:

- Baseline characteristics: Tables of demographics, diagnosis and extent of cancer, extramedullary involvement, bone marrow analysis, molecular response, prior TKI and non-TKI, patient disposition, analysis sets by stratum
- Exposure: Tables of duration of exposure, dose received
- Tables of concomitant medications as well as surgical and medical procedures
- PK (only in asciminib arm): Table and figure of asciminib concentration by time, table of asciminib PK parameters (patients with full PK sampling), figure of average trough asciminib concentration from week 2, 4, 12 and 24 vs. BCR-ABL ratio IS (%) at 24 weeks
- AEs: Tables of all AEs, treatment-related AEs, AEs requiring dose adjustment or interruption, AEs requiring additional therapies, serious adverse events (SAEs), adverse events of special interest (AESIs), overview table of AEs and death
- ECG: Tables of Notable ECG values, change from baseline in ECG parameters values
- Lab: Hematology shift table, biochemistry shift table
- Efficacy: Tables of molecular response categories at and by each time point, MMR rate at and by each time point, time to MMR, duration of MMR, cytogenetic response

categories at and by each time point, time to CCyR, duration of CCyR, TTF, PFS, OS. Figures of cumulative incidence of MMR and of CCyR, association between Week 1 Day 1 BCR-ABL1 gene mutation and clinical outcome.

